3.3 Protocol Adherence

Each investigator must adhere to the protocol detailed in this document and agree that any changes to the protocol must be approved by Internal Review Board (IRB). Each investigator will be responsible for enrolling only those study subjects who have met protocol eligibility criteria.

4. SUBJECT SELECTION

4.1 Inclusion and Exclusion Criteria

4.1.1 Inclusion Criteria

A subject will be eligible for participation in the **clinical trial** if they meet the following:

- 1. Ages 18 to 65 years;
- 2. History of SARS-CoV-2 PCR+ or COVID-19 Antigen Rapid Self-Test at least 2 months prior to study entry;
- 3. SARS-CoV-2 negative (PCR) at study entry;
- 4. Persistent cognitive difficulties (esp. "brain fog") that began around the time of the acute COVID-19;
- 5. At least two neurological and/or physical symptoms that started at COVID-19 infection and are ongoing at study entry, including fatigue, weakness, headache, loss of smell, tingling/numbness, shortness of breath, loss of appetite, palpitations/tachycardia, hair loss, musculoskeletal and/or chest pain;
- 6. Minimum score of 18 on the MMSE;
- 7. Education level, language skills, and literacy indicates participant is able to complete all assessments;

Randomized, Placebo-Controlled Parallel Group Clinical Trial of Nicotinamide Riboside to evaluate NAD+ Levels in Individuals with Persistent Cognitive and Physical Symptoms After COVID19 Illness ("Long-COVID")
Version 1.1

8. Willing and able to consent, complete all assessment and study procedures.

A subject will be eligible to participate as a **HC Participant** for a one time visit if they meet the following:

- 1. Ages 18 or older;
- 2. History of SARS-CoV-2 PCR+ or COVID-19 Antigen Rapid Self-Test+ at least 2 months prior to study entry;
- 3. SARS-CoV-2 negative (PCR) or COVID-19 Antigen Rapid Self-Test at study entry;
- 4. Experienced full recovery and does not have persistent cognitive difficulties, neurological and/or physical symptoms associated with COVID-19 infection;
- 5. Minimum score of 18 on the MMSE;
- 6. Education level, language skills, and literacy indicates participant is able to complete all assessments;
- 7. Willing and able to consent, complete all assessment and study procedures.

A subject will be eligible to participate as a **long-COVID Participant** for a one time visit if they meet the following:

- 1. Ages 18 or older;
- 2. History of positive SARS-CoV-2 PCR or COVID-19 Antigen Rapid Self-Test at least 2 months prior to study entry;
- 3. Negative COVID-19 Antigen Rapid Self-Test at study entry;
- 4. A minimum score of 18 on the Mini-Mental state examination;
- 5. Report persistent cognitive difficulties ("brain fog") that began around the time of the acute COVID19 illness;
- 6. At least two neurological and/or physical symptoms that started at COVID-19 infection and are ongoing at study entry, including fatigue, weakness, headache, loss of smell, tingling/numbness, shortness of breath, loss of appetite, palpitations/tachycardia, hair loss, musculoskeletal and/or chest pain;
- 7. Education level, language skills, and literacy indicates participant is able to complete all assessments;
- 8. Willing and able to consent, complete all assessment and study procedures.

4.1.2 Exclusion Criteria

A subject will not be eligible for participation in the **clinical trial** if they meet any of the following criteria:

- 1. Any specific CNS disease history, such as major clinical stroke, brain tumor, normal pressure hydrocephalus, multiple sclerosis, delirium, significant head trauma with persistent neurological of cognitive deficits or complaints;
- 2. Clinically significant unstable medical condition that could affect safety or compliance with the study and would, in the opinion of the investigator, pose a risk to the participant if they were to participate in the study;
- 3. Was intubated due to COVID-19;
- 4. History of neuroimaging with evidence of major infarction, injury, infection, or other focal lesions that may be related to cognitive dysfunction;
- 5. Major active or chronic unstable psychiatric illness (e.g. depression, bipolar disorder, obsessive compulsive disorder, schizophrenia) within the previous year;
- 6. Current suicidal ideation;
- 7. History of alcohol or other substance abuse or dependence within the past two years;
- 8. Any significant systemic illness or medical condition that could affect safety or compliance with study;
- 9. Laboratory abnormalities in Vitamin B12, Thyroid Stimulating Hormone (TSH), or other common laboratory parameters that might contribute to cognitive dysfunction or other abnormalities in hematological, hepatic or renal function tests;

Randomized, Placebo-Controlled Parallel Group Clinical Trial of Nicotinamide Riboside to evaluate NAD+ Levels in Individuals with Persistent Cognitive and Physical Symptoms After COVID19 Illness ("Long-COVID")

Version 1.1

- 10. Current use of medications with psychoactive properties that in the opinion of the principal investigator, may be deleteriously affecting cognition (e.g., anticholinergics, antihistamines, antipsychotics, sedative hypnotics, anxiolytics);
- 11. Any known hypersensitivity to nicotinamide riboside, or its principal metabolite, nicotinamide mononucleotide;
- 12. No consumption of dietary supplements containing more than 100mg of niacin, nicotinamide riboside (NR), or nicotinamide mononucleotide (NMN) as the primary agents 30 days prior to baseline and for the duration of the trial.
- 13. Use of other investigational agents or interventions one month prior to entry and for the duration of the trial;
- 14. If participating in the optional MRI sub-study: Any contraindication to undergo MRI studies, such as history of cardiac pacemaker or pacemaker wires, metallic particles in the body, vascular clips in the head, prosthetic heart valves, and/or severe claustrophobia impeding ability to participate in an imaging study;
- 15. Pregnant people or those who are planning to become pregnant within 7 months from study entry.

A subject will not be eligible to participate as a **HC participant** if they meet any of the following criteria:

- 1. Any specific CNS disease history, such as major clinical stroke, brain tumor, normal pressure hydrocephalus, multiple sclerosis, delirium, significant head trauma with persistent neurological of cognitive deficits or complaints;
- 2. Clinically significant unstable medical condition that could affect safety or compliance with the study and would, in the opinion of the investigator, pose a risk to the participant if they were to participate in the study;
- 3. Was intubated due to COVID-19:
- 4. History of neuroimaging with evidence of major infarction, injury, infection, or other focal lesions that may be related to cognitive dysfunction;
- 5. Major active or chronic unstable psychiatric illness (e.g. depression, bipolar disorder, obsessive compulsive disorder, schizophrenia) within the previous year;
- 6. Current suicidal ideation;
- 7. History of alcohol or other substance abuse or dependence within the past two years;
- 8. Any significant systemic illness or medical condition that could affect safety or compliance with study;
- 9. Current use of medications with psychoactive or other properties that in the opinion of the principal investigator, may be deleteriously affecting cognition (e.g., anticholinergics, antihistamines, antipsychotics, sedative hypnotics, anxiolytics);
- 10. If 65 years of age or younger, have any contraindication to undergo MRI studies, such as history of cardiac pacemaker or pacemaker wires, metallic particles in the body, vascular clips in the head, prosthetic heart valves, and/or severe claustrophobia impeding ability to participate in an imaging study;
- 11. Pregnant individuals.

A subject will not be eligible to participate as an **long-COVID Participant** if they meet any of the following criteria:

- 1. Any specific CNS disease history, such as major clinical stroke, brain tumor, normal pressure hydrocephalus, multiple sclerosis, delirium, significant head trauma with persistent neurological of cognitive deficits or complaints;
- 2. Clinically significant unstable medical condition that could affect safety or compliance with the study and would, in the opinion of the investigator, pose a risk to the participant if they were to participate in the study;
- 3. Was intubated due to COVID-19:

Randomized, Placebo-Controlled Parallel Group Clinical Trial of Nicotinamide Riboside to evaluate NAD+ Levels in Individuals with Persistent Cognitive and Physical Symptoms After COVID19 Illness ("Long-COVID")

Version 1.1

- 4. History of neuroimaging with evidence of major infarction, injury, infection, or other focal lesions that may be related to cognitive dysfunction;
- 5. Major active or chronic unstable psychiatric illness (e.g. depression, bipolar disorder, obsessive compulsive disorder, schizophrenia) within the previous year;
- 6. Current suicidal ideation;
- 7. History of alcohol or other substance abuse or dependence within the past two years;
- 8. Any significant systemic illness or medical condition that could affect safety or compliance with study;
- 9. Current use of medications with psychoactive or other properties that in the opinion of the principal investigator, may be deleteriously affecting cognition (e.g., anticholinergies, antihistamines, antipsychotics, sedative hypnotics, anxiolytics);
- 10. If 65 years of age or younger, have any contraindication to undergo MRI studies, such as history of cardiac pacemaker or pacemaker wires, metallic particles in the body, vascular clips in the head, prosthetic heart valves, and/or severe claustrophobia impeding ability to participate in an imaging study;
- 11. Pregnant individuals.

4.1.2.1 Individuals of Childbearing Age

Individuals of childbearing age will be eligible for the study. However, pregnant individuals will be ineligible for the clinical trial and sub-studies studies, and those who are planning to become pregnant within 7 months from study entry will be ineligible for the clinical trial.

4.2 Recruitment

Approximately 120 subjects with long-COVID will be screened, and after screening, approximately 100 subjects are expected to complete the clinical trial. Approximately 75 healthy controls (50 participants ≤65 years of age, and 25 participants <65 years of age) and 75 long covid participants (50 participants <65 years of age, and 25 participants ≥65 years of age) are expected to complete the one-time visit. All subjects in the long-COVID group participating in the clinical trial will be given the option to participate in the optional repeat MRI sub-study until 24 subjects have completed the sub-study, and 50 more can complete the baseline MRI. All 50 healthy controls and 50 long-COVID participants ≤65 years of age are required to complete the MRI at their one-time visit. Individuals older than 65 years will not complete an MRI.

4.2.1 Recruitment of Subjects through Advertising

Advertisement flyers will be posted on bulletin boards around MGH (both the main campus and Charlestown campus) to advertise for the study as well as ad advertisement on Partners Rally for Research. Advertisement flyers will also be provided at community events (e.g., health fairs) and other institutions (e.g., churches, community centers). An email address and phone number will be provided that will ring directly to the research coordinator, and voice messages can be left for the coordinator on a password-protected voice mailbox. Additionally, for participants collected through Rally, we will email them a survey to complete via REDCap using send secure. This digital survey will allow us to assess their eligibility. Once participants submit the survey and are deemed eligible, we will contact them by phone to ask any follow-up questions, collect more information as needed, and schedule them for an in-person visit. We may still pre-screen people by phone if the person communicates that this is their preferred method.

4.2.2 Recruitment of Subjects Identified through Private Medical Information

The Neuro-Infectious Diseases Unit, Neurology Clinic, Psychological Assessment Center, Multicultural Assessment and Research Center, MGH Primary Care clinics, the NeuroScience dashboard, and Neuropsychiatric Clinic physicians will be made aware of the study, including eligibility criteria. If they feel

Randomized, Placebo-Controlled Parallel Group Clinical Trial of Nicotinamide Riboside to evaluate NAD+ Levels in Individuals with Persistent Cognitive and Physical Symptoms After COVID19 Illness ("Long-COVID")

Version 1.1

that a patient of theirs may be a candidate for the study, they will obtain the patient's permission to be contacted by the study staff or provide a flyer with the study's information. Those who agree to be contacted will be contacted by the study coordinator who will explain the study in further detail and if the subject is interested, potentially complete a telephone or online prescreening survey.

4.2.3 Recruitment of Subjects from the MGH McCance Center for Brain Health

Some subjects will be recruited from the study titled "Brain Health in COVID-19 survivors and their caregivers" at the MGH McCance Center for Brain Health (IRB protocol 2020P001455).

4.2.4 Recruitment of Subjects from Among the Investigators' Own Patients

[name] (co-investigator) is a neurologist in the MGH Memory Disorders Unit and [name] a neuropsychologist at the Multicultural Assessment and Research Center. Subjects may also be recruited from among their patients. Special care will be taken to ensure patients are aware that their participation is completely voluntary and that their decision to participate will not affect their care. [name] and [name] will obtain the patient's permission to be contacted by the study staff or provide a flyer with the study's information. If interested, the patient will be contacted by the study coordinator who will explain the study in further detail and if the subject is interested, potentially complete a telephone or online prescreening survey.

5. SUBJECT ENROLLMENT

5.1 Informed Consent Process

This study will be conducted in compliance with Title 21 Part 50 of the United States of America Code of Federal Regulations (CFR), Federal Regulations, and ICH Guidance Documents pertaining to informed consent.

Potential subjects will be given general information about the research (e.g., through informational sheets, letters, or discussion with their treating physicians). If they are interested in learning more about the study, they will then contact the research coordinator. The research coordinator will obtain verbal consent in accordance with Partner's Prescreening Guidelines prior to performing a telephone prescreening interview. Subjects who meet pre-screening criteria for the clinical trial and wish to continue the screening process will be scheduled for a screening visit that will take place in person at MGH CNY campus. Subjects who are eligible as HC or long-COVID participants based on the phone screening will be scheduled for their one-time visit that will take place in person at MGH CNY campus.

At the clinical trial's screening visit and the one time visit for the HC and long-COVID participants, the investigator will meet with the potential subject to review and discuss the details of the study using the informed consent document as a guide. A copy of the informed consent document will be sent to the subject before the first visit takes place, and they will have at least 24 hours between when the document is received and when the first visit is scheduled in order for the subject to have adequate time to fully review the Informed Consent Document.

The informed consent process will be conducted using a REDCap-based electronic consent form. The consent form has been developed in REDCap, a secure, web-based, HIPAA-compliant, data collection platform with a user management system allowing project owners to grant and control varying levels of access to data collection instruments and data for other users. If requested by the subject, a traditional hard copy consent form will be provided to the subject along with any materials needed for return shipping.

Randomized, Placebo-Controlled Parallel Group Clinical Trial of Nicotinamide Riboside to evaluate NAD+ Levels in Individuals with Persistent Cognitive and Physical Symptoms After COVID19 Illness ("Long-COVID")

Version 1.1

During the first visit, the informed consent document will be reviewed with the participant by a licensed clinician investigator. The potential subject may ask to speak with the physician investigator should a non-physician investigator be involved in obtaining informed consent. The informed consent discussion will include all of the required elements of informed consent, including the purpose of the research, the procedures to be followed, the risks and discomforts, as well as potential benefits associated with participation, and alternative procedures to study participation. Their questions will be answered to their satisfaction. The subject will be provided with adequate time to reflect on the potential benefits and risks and possible discomforts of participation, and to make an informed decision.

If the subject agrees to participate in the study, a link will be sent to the REDCap e-consent form or the subject will sign the provided hard-copy informed consent form. For REDCap e-consent, subject signatures will be obtained using electronic signature via mouse followed by electronic signature by the doctorate-level clinician investigator. The signed hard-copy consent forms will then be signed by the consenting investigator. Upon completion of the informed consent process, subjects will be provided with a hard copy of the signed consent from and hard copies will be stored in each subject's binder.

All subjects must be deemed capable of providing informed consent by the Investigators. Subjects who are not deemed capable of providing informed consent will be excluded from this study.

5.2 Remuneration

Subjects for the clinical trial will receive \$20 for their participation in each visit. If subjects elect to participate in MRIs, they will receive \$100 for each MRI. Subjects who are part of the clinical trial will also receive \$20 upon completion of the study as long as they were at least 80% compliant with all study activities, including taking their medication, completing cognitive tests, and completing the Fitbit activity tracking. Therefore, if a subject elects to undergo all additional procedures, the maximum amount a subject would be eligible to receive is \$320 at study completion. If a subject does not elect to participate in any optional procedures but is compliant with study tasks, they would be eligible to receive \$120. We anticipate some subjects may come from outside the region and if so, appropriate travel expenses may be reimbursed including transportation up to \$15 per visit. To minimize the inconvenience of frequent visits, meal and parking vouchers for use at the MGH Charlestown Navy Yard (CNY) facilities will also be offered at each visit.

Long-COVID and HC participants who are 65 years of age or younger will receive \$120 for their participation in the one-time visit. If they live outside the region, appropriate travel expenses may be reimbursed including transportation up to \$15 for the visit. Meal and parking vouchers for use at the MGH CNY cafeteria and parking garage will also be offered.

Long-COVID and HC participants who are older than 65 years of age, we will pay \$80 for their participation in the one-time visit. If they live outside the region, appropriate travel expenses may be reimbursed including transportation up to \$60 for the visit. Meal and parking vouchers for use at the MGH CNY cafeteria and parking garage will also be offered.

5.3 Randomization

Subjects in the clinical trial will be randomized into one of two groups (see Figure 4 below). Randomization will be done by MGH Clinical Trials Pharmacy.

Screening (Week 0)	Baseline (Week 2)	Visit 1 (Week 7)	Visit 2 (Week 12)	Visit 3 (Week 17)	Visit 4 (Week 22)	Follow-up (Week 24)
Placebo (Lead-in)	N = 60 NR N = 100	NR	NR	NR	NR	
Placebo (Lead-in)	N = 100 $N = 40$ Placebo	Placebo	NR	NR	NR	

Figure 4. Study Schema

5.4 Reasons for Withdrawal

A study subject will be discontinued from participation in the study if:

- Any clinical adverse event (AE), concurrent illness, or other medical condition or situation occurs such that continued participation in the study would not be in the best interest of the subject.
- The subject meets any exclusion criteria (either newly developed or not previously recognized).
- Tests positive for SARS-CoV-2 PCR or COVID-19 Antigen Rapid Self-Test
- The subject is less than 80% or greater than 120% compliant with NR dosing.

Subjects are free to withdraw from participation in the study at any time upon request.

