5.4.1 Handling of Withdrawals

A subject may choose to discontinue participation in the study at any time. An Early Termination visit will occur when a subject withdraws consent, i.e. withdrawing his or her participation in future study procedures.

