6.2.3 Follow Up Visits (Weeks 7, 12 and 17)

These visits will take place every 5 weeks (± 2 days) following Baseline.

Randomized, Placebo-Controlled Parallel Group Clinical Trial of Nicotinamide Riboside to evaluate NAD+ Levels in Individuals with Persistent Cognitive and Physical Symptoms After COVID19 Illness ("Long-COVID")
Version 1.1

¹These procedures can take place virtually via Zoom videoconference if necessary.

- Review and document concomitant medications, supplements, and therapies¹
- Assess COVID-19 related symptoms
- Perform physical assessments
- Perform physical and neurological examination
- Measure vital signs
- Dispense study supplement or PBO¹
- Assess study supplement compliance
- Administer battery of cognitive assessments (only week 12)
- Administer questionnaires about neuropsychiatric symptoms, sleep, physical activity and others
- Blood draw and a collect dried blood spot sample for biomarker analysis
- Assess and document adverse events (AEs) and changes to medical history¹

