6.2.5 Early Termination Visit

If the subject withdraws from the study before completion of all study visits, they will be invited to participate in an Early Termination Visit within 7 days of stopping treatment.

- Measure Vital Signs
- Perform physical and neurological examination
- Blood draw and a collect dried blood spot sample for biomarker analysis
- Assess study supplement compliance
- Assess COVID-19 related symptoms
- Administer cognitive assessments
- Administer questionnaires about neuropsychiatric symptoms, sleep, physical activity, and others
- Assess and document AEs and changes to medical history¹
- Review and document concomitant medications, supplements, and therapies¹
- Perform optional MRI scan

Randomized, Placebo-Controlled Parallel Group Clinical Trial of Nicotinamide Riboside to evaluate NAD+ Levels in Individuals with Persistent Cognitive and Physical Symptoms After COVID19 Illness ("Long-COVID")

Version 1.1

¹These procedures can take place virtually via Zoom videoconference if necessary.

¹These procedures can take place virtually via Zoom videoconference if necessary.

¹These procedures can take place virtually via Zoom videoconference if necessary.

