7.1.2.2.2 Repeatable Battery for the Assessment of Neuropsychological Status (RBANS)

The Repeatable Battery for the Assessment of Neuropsychological Status (RBANS)²⁴ is a commonly used 25-minute, standardized neurocognitive battery assessing functioning across multiple cognitive domains. It is designed to be administered repeatably, with several equivalent alternate forms available. The RBANS measures a total of five neurocognitive domains using twelve subtests: immediate memory (List Learning and Story Memory), visuospatial/constructional (Figure Copy and Line Orientation), language (Picture naming and Semantic Fluency), attention (Digit Span and Coding), and delayed memory (List Recall, List Recognition, Story Memory, and Figure Recall). The RBANS will be administered at Baseline, Week 12, and End of Study (Week 22) using alternate forms.

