9.1 Primary analysis

For all outcomes, we will perform intention-to-treat (ITT) analysis and mixed-effects model repeated measures (MMRM). Group (NR-NR vs. PBO-NR sequence), time, and group by time interactions will be included in the MMRM as fixed effects. The study's outcomes will be the change score of ECog, RBANS, and TMT-B from baseline, and the change in NAD+ levels from baseline. We also will examine changes in the FSS, BAI, BDI, and PSQI scores. An unstructured covariance matrix will be used to account for the correlation of repeated measures within a participant. Age, sex, and education will be included in the models as covariates.

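### Section 5.4 ends study participation, not only the supplement, when an exclusion criterion is newly met; removal before Week 12 then leaves no post-baseline RBANS or TMT-B unless an Early Termination visit is attended

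*Combined protocol and SAP*

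**What the plan says.** The list of triggers in section 5.4 opens with "A study subject will be discontinued from participation in the study if". One trigger is that "The subject meets any exclusion criteria (either newly developed or not previously recognized"). The schedule in 6.1 repeats the eligibility review at Weeks 2, 7, 12, 17 and 22, so the rule operates after randomisation.

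Three of the clinical-trial exclusions in 4.1.2 touch what is being measured:
- Criterion 5 is active or unstable psychiatric illness, with depression among its examples.
- Criterion 6 is current suicidal ideation.
- Criterion 10 is psychoactive medication that the principal investigator thinks may be harming cognition. Its examples include anxiolytics and sedative hypnotics.

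Section 9.1 states that for all outcomes "we will perform intention-to-treat (ITT) analysis and mixed-effects model repeated measures (MMRM"). The "outcomes will be the change score of ECog, RBANS, and TMT-B from baseline", together with change in NAD+; BDI and BAI are also examined.

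On timing, section 7.1.2.2.2 says "The RBANS will be administered at Baseline, Week 12, and End of Study (Week 22) using alternate forms". For the visits at Weeks 7, 12 and 17, section 6.2.3 says "Administer battery of cognitive assessments (only week 12"). ECog, BDI and BAI are taken at every visit (3.2.1), and blood for NAD+ every five weeks from Week 2.

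On leaving early, section 5.4.1 says "An Early Termination visit will occur when a subject withdraws consent". Section 6.2.5 says of those who withdraw that "they will be invited to participate in an Early Termination Visit within 7 days of stopping treatment".

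**The concern.** An intention-to-treat analysis should go on collecting outcomes after treatment stops, above all when the reason for stopping is related to an outcome. Section 5.4 does the reverse: it ends follow-up as well as dosing. Criteria 5 and 6 overlap the BDI, and the overlap of criterion 6 is direct, because Question 9 of that scale is the suicidality screen (10.1.1). Criterion 10 overlaps the cognitive outcomes through its wording, and mood, anxiety and sleep only through its example drugs.

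The placebo group crosses to NR at Week 12 (3.1 and Figure 4), so Week 12 is the last placebo-controlled assessment and the only scheduled post-baseline one for RBANS and TMT-B. Missing it leaves no change score for that contrast. A recorded Week 7 BDI does not fill the gap, because each model in 9.1 takes one outcome with age, sex and education as covariates. Section 9 has no missing-data or sensitivity plan.

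**Working it through.** **What is on record if a participant is removed after Week 2 and before Week 12**

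| Outcome | Week 2 | Week 7 | Week 12 |
|---|---|---|---|
| ECog, BDI, BAI, NAD+ | yes | yes, if removed at or after that visit | lost |
| RBANS, TMT-B | yes | not scheduled | lost |

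An attended Early Termination visit supplies both rows, since 6.2.5 includes the cognitive assessments, questionnaires and blood. Section 9 does not say how such a value would be placed against Week 12.

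**Size: inputs.** The plan gives 60 NR and 40 placebo-then-NR participants (3.1). It gives no SD, effect size or removal rate, so there is no figure of its own to reproduce. Everything else here is assumed:
- Outcomes have unit SD, and NR improves both mood and cognition by 0.4 SD.
- A participant is removed when the mood score M is worse than c, with c = 2 or 1.5 SD.
- The mood-cognition correlation r is 0.3 (range 0.1 to 0.5).

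**Standard error (SE) of the contrast.** sqrt(1/60 + 1/40) = 0.204 SD.

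**Removals before Week 12.** M is N(0,1) on placebo and N(-0.4,1) on NR.
- c = 2: placebo 40 × 0.0228 = 0.9; NR 60 × 0.0082 = 0.5; total 1.4 of 100.
- c = 1.5: placebo 40 × 0.0668 = 2.7; NR 60 × 0.0287 = 1.7; total 4.4 of 100.

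**Shift in mean mood among those retained.** This is phi(c)/Phi(c) on placebo and phi(c + 0.4)/Phi(c + 0.4) on NR.
- c = 2: 0.0552 - 0.0226 = 0.0327 SD (from unrounded values).
- c = 1.5: 0.1388 - 0.0676 = 0.0712 SD.

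**RBANS and TMT-B bias = r × difference in shift, Early Termination visit missed.**

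| | c = 2 | c = 1.5 |
|---|---|---|
| Bias at r = 0.3 | 0.0098 SD | 0.0214 SD |
| As share of 0.4 SD | 2.5% | 5.3% |
| In SE | 0.05 | 0.10 |
| Range in SE, r = 0.1 to 0.5 | 0.02 to 0.08 | 0.03 to 0.17 |
| Share if half attend Early Termination (r = 0.3) | 1.2% | 2.5% |

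With a mood effect of 0.2 or 0.6 SD instead of 0.4 (r = 0.3), the bias is 0.0058 or 0.0125 SD at c = 2, and 0.0121 or 0.0282 SD at c = 1.5.

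**No mood effect.** Both arms shift equally, so the bias is 0. Removals are 2.3 or 6.7 of 100, and the SE rises by 1/sqrt(0.9772) - 1 = 1.2% or 1/sqrt(0.9332) - 1 = 3.5%.

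**BDI and BAI at Week 12.** These come from a two-visit repeated-measures model on 2,000,000 simulated participants per arm (true effect 0.400 SD, Week 7 to Week 12 correlation 0.7, Monte Carlo error about 0.001 SD). Estimates are for c = 2 / c = 1.5.
- Worsened score recorded at Week 7: 0.401 / 0.399, so no bias.
- Removed between Weeks 7 and 12 with nothing recorded: 0.383 / 0.359.
- The same, with half attending an Early Termination visit: 0.392 / 0.383.
- Removed before Week 7 with nothing recorded: 0.376 / 0.351.

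The largest attenuation, over correlations of 0.5 to 0.8, is about 14%: 0.14 × 0.4 = 0.056 SD, or 0.27 SE. The nothing-recorded cases are upper bounds, because they put every removal in an unrecorded window.

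**The case against.** Much of the protocol is softer than 5.4. Dosing alone may be suspended (8.4), and 8.4.1 implies that someone who stops the supplement may remain. Non-compliance is a mandatory trigger in 5.4, yet 8.5 provides retraining and leaves persistent cases to the principal investigator, which suggests that 5.4 is a summary list. Section 11.3.1 makes the investigators responsible for removal decisions. The Early Termination visit includes the cognitive battery, and attendance cannot be compelled in any trial. Removing someone newly suicidal or psychiatrically unstable is a defensible safety choice.

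Most of this stands as mitigation. It does not cancel the rule: 5.4 has no option to stop the supplement and stay for a newly met exclusion, and no other section supplies one for that case. A site following 5.4 literally would lose data that 8.4.1 implies could be kept.

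Three stronger readings are tempting but unsupported:
- A reader might infer that removed participants drop out of the intention-to-treat analysis altogether. They do not: recorded values stay in the model, including Week 7 ECog, NAD+, BDI and BAI, and Week 2 RBANS and TMT-B exist.
- A reader might infer that a bad mood score triggers removal. No section ties a score to discontinuation; a positive answer to BDI Question 9 leads to clinical evaluation and triage, and criterion 10 rests on the investigator's opinion. The cut-offs above are modelling devices.
- A reader might treat criterion 10 as a mood criterion. It is worded around cognition.

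**Conclusion.** The point holds as a modest, cheaply corrected weakness. The loss of post-baseline RBANS and TMT-B after a removal between Weeks 2 and 12, absent an Early Termination visit, follows directly from the text and schedule. Its size does not: the removal frequency is not stated and every input beyond the 60/40 split is assumed. On those inputs the RBANS and TMT-B bias is about 0.05 to 0.10 SE at r = 0.3, and at most 0.17 SE over the range of correlations shown. It runs toward no effect when NR helps both mood and cognition. If NR does not affect mood, the bias is zero, no false positive arises from this source, and only precision is lost. For BDI and BAI, a worsened score recorded at Week 7 removes the bias. This does not threaten the trial's validity.

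**What to change.** Amend 5.4 so that a newly met exclusion criterion after randomisation leads to a decision on the supplement under 8.4. The participant then stays in scheduled assessments through at least Week 12 (cognitive battery, questionnaires and blood), unless consent is withdrawn or the investigator judges the assessments unsafe. Apply the same wording to the other post-randomisation triggers listed there (adverse events or illness, a positive SARS-CoV-2 test, non-compliance), because removal for those reasons loses the same Week 12 data.

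Amend 5.4.1 so that Early Termination assessments, including the cognitive battery, are sought after removal by the investigator as well as after withdrawal of consent.

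The cost is amendment wording and a few extra visits for participants off supplement. For the exclusion-criterion trigger this is about 1 to 7 of 100 on the assumed cut-offs, at $20 plus up to $15 travel per visit (5.2). The other triggers would add a number that the documents do not give, and staff and assay costs are not stated. There is also some testing burden for unwell participants, since 10.1.1 acknowledges that testing can cause anxiety and fatigue; the safety exception covers that.
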